**Table 9: Clinical Laboratory Parameters** 

Hematology	Serum Chemistry				
Red blood cell count	Serum creatinine				
Hemoglobin	BUN				
Hematocrit	Glucose (non-fasting)				
White blood cell count	Albumin				
Differential:	AST				
Neutrophils	ALT				
ANC	LDH				
Lymphocytes	Total bilirubin				
Monocytes	Total protein				
Eosinophils	Alkaline phosphatase				
Basophils	Calcium				
Platelets	Phosphorus				
	Magnesium				
	Sodium				
	Potassium				
	Chloride				
	Bicarbonate				

#### 10.3. Adverse and Serious Adverse Events

#### **10.3.1.** Definition of Adverse Events

#### **10.3.1.1.** Adverse Event (AE)

An adverse event (AE) includes any noxious, pathological, or unintended change in anatomical, physiological, or metabolic functions as indicated by physical signs, symptoms, and/or laboratory changes occurring whether or not temporally associated with study drug administration and whether or not considered related to study drug. This definition includes an exacerbation of pre-existing medical conditions or events, intercurrent illnesses, hypersensitivity reactions, drug interactions, or clinically significant laboratory findings.

An AE does not include the following:

- Medical or surgical procedures, e.g., tooth extraction, transfusion, surgery (The medical condition that leads to the procedure is to be recorded as an AE.)
- Pre-existing conditions or procedures present or detected at the start of the study that do not worsen

Confidential 51
December 31, 2019 Protocol Amendment 4

• Hospitalization for elective surgeries or for other situations in which an untoward medical event has not occurred

- Abnormal laboratory value, unless it is clinically significant
- Overdose of study drug or concomitant medication unaccompanied by signs/symptoms (If sign/symptoms occur, the final diagnosis should be recorded as an AE.)
- Pregnancy by itself, unless a complication occurs during pregnancy leading to hospitalization; in this case (The medical condition that leads to the hospitalization is to be recorded as the AE.)
- A significant worsening of the disease under investigation which is captured as an efficacy parameter in this study and, thus, is not to be recorded as an AE.

#### 10.3.1.2. Serious Adverse Event (SAE)

A serious adverse event (SAE) is defined as an adverse event that results in any of the following outcomes:

- Death
- Life-threatening, i.e., immediate risk of death from the event as it occurred; (This does not include an adverse event that, had it occurred in a more serious form, might have caused death.)
- Persistent or substantial disability/incapacitation
- Results in or prolongs an existing inpatient hospitalization
- Congenital anomaly/birth defect

Important medical events that may not result in death, be life-threatening, or require hospitalization may be considered serious when, based on medical judgment, they may jeopardize the subject or may require medical or surgical intervention to prevent one of the outcomes listed in this definition.

#### 10.3.1.3. Unexpected Adverse Event

An AE or suspected adverse reaction is considered "unexpected" if it is not listed in the Investigator's Brochure or is not listed at the specificity or severity that has been observed; or, is not consistent with the risk information described in the protocol or elsewhere. For example, under this definition, hepatic necrosis would be unexpected (by virtue of greater severity) if the Investigator's Brochure referred only to elevated hepatic enzymes or hepatitis. Similarly, cerebral thromboembolism and cerebral vasculitis would be unexpected (by virtue of greater specificity) if the Investigator's Brochure listed only cerebral vascular accidents.

"Unexpected," as used in this definition, also refers to AEs or suspected adverse reactions that are mentioned in the Investigator's Brochure as occurring with a class of drugs or as anticipated from the pharmacological properties of the investigational therapy but are not specifically mentioned as occurring with the investigational therapy.

Confidential 52
December 31, 2019 Protocol Amendment 4

#### 10.3.1.4. Adverse Event Reporting Period

The adverse event reporting period begins from the date of the first dose of study drug(s) to 28 days following the last dose of study drug(s).

#### 10.3.1.5. Recording of Adverse Events

Each AE should be recorded in standard medical terminology on the AE CRF module. Whenever possible, the AE should be evaluated and reported as a diagnosis rather than as individual signs or symptoms. For example, cough, runny nose, sneezing, sore throat, and head congestion should be reported as 'upper respiratory infection'. If a definitive diagnosis is not possible, the individual signs and symptoms should be recorded. Dates of start (onset) and stop (recovery), action taken, and outcome will be recorded in the AE CRF module.

All clinically significant abnormal changes in laboratory parameters will be recorded as an AE on the AE module, with the following exceptions: clinically significant abnormal laboratory changes determined to be related to the study condition and concomitant conditions, e.g., diabetes, of which the investigator was previously aware and that have not worsened.

The investigator will evaluate all AEs with regard to maximum intensity and relationship to study drug, as follows.

#### 10.3.1.5.1. Maximum Intensity

Maximum intensity should be assigned using one of the severity grades as outlined in the National Cancer Institute Common Terminology Criteria for Adverse Events (NCI CTCAE v4.03); if the AE is not specifically listed in CTCAE v4.03, use the following grades:

- Grade 1: mild
- Grade 2: moderate
- Grade 3: severe
- Grade 4: life-threatening or disabling
- Grade 5: death

#### 10.3.1.5.2. Relationship to Study Drug

The degree of certainty with which an AE is attributed to study drug (or alternative causes, e.g., natural history of the underlying diseases, concomitant therapy, etc.) will be determined by how well the event can be understood in terms of known pharmacology of the study drug and/or reactions of similar nature previously observed with study drug. Each AE will be assigned one of the following five categories:

Not related: There is not a temporal relationship to the study drug (e.g., too early, too late), or there is a reasonable causal relationship to another drug, concurrent illness, or circumstance.

• *Unlikely related*: There is a temporal relationship to study drug, but there is not a reasonable causal relationship between the time of study drug administration and the AE (i.e., it is doubtful the AE is related to the study drug); could be reasonably explained by other

Confidential 53
December 31, 2019 Protocol Amendment 4

factors, including underlying disease, complications, concomitant drugs, or concurrent treatment.

- Possibly related: There is a reasonable temporal sequence from time of study drug administration (e.g., occurred in a time frame relevant to study drug dose); or for which the possibility of the study drug being the causative factor (e.g., existence of similar reports attributed to the study drug; reactions attributable to the pharmacological effect) could not be excluded, although other factors such as underlying disease, complications, concomitant drugs, or concurrent treatment are presumable.
- *Probably related*: There is a reasonable temporal sequence from time of study drug administration; and for which the possibility of factors other than the study drug administration, such as underlying disease, complications, concomitant drugs, or concurrent treatment, could not be excluded as the cause.
- Definitely related: Follows a clear temporal sequence from time of study drug administration; could not be possibly explained by the known characteristics of the subject's clinical state, environmental or toxic factors, or other modes of therapy administered to the subject; follows a response pattern known to be associated with study drug administration.

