# 5.5.1.2. Dose Modifications and Dose Reductions

Dose-limiting toxicity (DLT) is defined as any one of the following events:

- Grade 4 hematologic toxicity for > 1 day
- Grade 3 hematologic toxicity with complications (e.g., thrombocytopenia with bleeding)
- Failure of Grade 3 thrombocytopenia, absolute neutrophil count (ANC), hemoglobin to recover to Grade ≤ 1 within 4 weeks despite the use of platelet and red blood cell (RBC) transfusions and/or growth factors
- ≥ Grade 3 non-hematologic toxicity not due to disease progression (excluding Grade 3 nausea, vomiting or diarrhea that is adequately controlled with supportive care and resolves to ≤ Grade 2 within 48 hours, or Grade 3 electrolyte disturbances responsive to correction within 24 hours)
- $\geq$  Grade 3 liver function tests (LFTs) lasting > 72 hours
- Treatment interruption > 14 days due to toxicity
- Other important medical event

Subjects who require a dose reduction due to toxicity will be considered to have had a DLT.

No DLTs were experienced in the Monotherapy Safety Run-in Phase and no dose reductions were required for toxicity. If a DLT is experienced in  $\geq 2$  of 6 subjects in the Combination Safety Run-in Phase during Cycle 1, no further subjects will be enrolled at that dose level. Subjects who experience a DLT may continue treatment at the next lower dose level until disease progression or

Confidential 33
December 31, 2019 Protocol Amendment 4

unacceptable toxicity. The MTD is defined as the doses of E6201 plus dabrafenib at which  $\leq$  1 of 6 subjects experiences a DLT.

Subjects who experience E6201- and/or dabrafenib-related toxicity requiring a dose reduction may continue treatment at the next lower dose level for either drug until disease progression or unacceptable toxicity. Adverse events considered for dose reduction should not include the events assessed by the investigator as exclusively related to underlying disease or other medical condition or concomitant treatment. If treatment must be delayed for reasons other than toxicity, contact the Medical Monitor to discuss the reasons for delay and plans for resuming study therapy.

The E6201 dose modification guidelines are outlined in Table 4. Provisions are not made for dose levels below 160 mg/m² twice weekly. If 160 mg/m² twice weekly is determined to be unsuitable based on toxicity as defined above, the subject will be permanently discontinued from E6201 treatment.

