#### 11.3.1. **Safety Analysis**

#### 11.3.1.1. Adverse Events

All safety endpoints will be summarized using descriptive statistics and will be based on the FAS dataset.

All AEs will be coded based on the Medical Dictionary for Regulatory Affairs (MedDRA; Version 17.0 or higher). An AE will be considered a treatment emergent adverse event (TEAE) if the onset is after the first dose of study drug or if the condition was present at baseline but worsened after the first dose.

All AEs for each subject will be listed, including intensity grading, relationship to study drug, action taken and outcome. Subject listings of deaths, SAEs, and AEs leading to treatment discontinuation will be provided. Subject narratives will be provided for deaths, SAEs and other significant AEs. Summary tables will be prepared to examine TEAE severity and relationship to study treatment.

Confidential 57 December 31, 2019 Protocol Amendment 4

AE summaries will be produced separately for each dose cohort and overall, each disease cohort by dose and overall, and by monotherapy combination phases of the study. All summaries will show, by subject group, dose cohort and overall, the number and percentage of subjects experiencing at least 1 TEAE of each preferred term, arranged by system organ class, and the number of occurrences of the event. Separate summaries will be produced by relationship to study medication, by severity, and for those events with an incidence rate of at least 2% in any group or overall.

SAEs will be summarized in a similar manner; overall, by relationship to study medication, and by severity.

In addition to the above, summaries of the number and percentage of subjects discontinuing the study due to AEs and, due to death, will be presented.

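### The Probably related category is worded so that excluding other causes bars an event from it, and causality is rated once against an undefined study drug in a two-drug regimen

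*Combined protocol and SAP*

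**What the plan says.** Section 10.3.1.5 sets the task: "The investigator will evaluate all AEs with regard to maximum intensity and relationship to study drug, as follows". Section 10.3.1.5.2 presents the scale as a measure of certainty ("The degree of certainty with which an AE is attributed to study drug") and calls for a single choice: "Each AE will be assigned one of the following five categories".

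Three of the five definitions matter here.

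- *Possibly related*: reasonable timing, or a drug role that cannot be ruled out, "although other factors such as underlying disease, complications, concomitant drugs, or concurrent treatment are presumable".
- *Probably related*: reasonable timing, and other factors, including "concomitant drugs, or concurrent treatment, could not be excluded as the cause".
- *Definitely related*: clear timing, no other possible explanation, and a response pattern already known for the drug.

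The definition of *Not related* includes events with a reasonable causal link to another drug.

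Elsewhere attribution is by drug. Sections 5.1 and 5.5.1.2 reduce E6201 for suspected E6201 toxicity and dabrafenib for suspected dabrafenib toxicity; the wording in 5.5.1.2 is "Subjects who experience E6201- and/or dabrafenib-related toxicity requiring a dose reduction may" continue at a lower level of either drug. Table 4 is limited to E6201-related toxicity. Section 10.3.1.6 asks for SAEs later than 28 days after the last dose only if they are thought related to one of the two named drugs.

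For reporting, 11.3.1.1 states: "Summary tables will be prepared to examine TEAE severity and relationship to study treatment". It also plans TEAE and SAE summaries by relationship. The synopsis lists the same endpoints, uses the plural for the medications, and leaves details to a statistical analysis plan. Neither place specifies a table per drug or says which categories count as related.

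**The concern.** A certainty scale should move an event up as competing explanations fall away. Here the second-highest category requires that competing explanations remain open. An investigator who has worked an event up and excluded other causes cannot use Probably, and can use Definitely only if the pattern is already known. For a new combination, some reactions may have no known pattern yet.

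The second problem is the object of the rating. E6201 and dabrafenib are given together, but the section refers to a single study drug without saying whether that means E6201, dabrafenib or the regimen. Two investigators can code the same event differently and both follow the text. At stake is how the relationship tables are read, and these tables serve the secondary objective on the safety of E6201 alone and with dabrafenib.

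**Working it through.** No power or alpha figure is involved. The check treats the definitions as logical conditions and then counts the subjects affected.

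**Conditions.** T = reasonable timing. D = drug role cannot be ruled out. P = other factors presumable. E = other causes excluded. K = known response pattern.

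- Possibly, as punctuated (reading A): T or (D and P).
- Possibly, if the clause on other factors governs both limbs (reading B): (T or D) and P.
- Probably: T and not E.
- Definitely: T (clear) and E and K.

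| Event | Possibly, A | Possibly, B | Probably | Definitely |
|---|---|---|---|---|
| 1. T, not E, P | yes | yes | yes | no |
| 2. T, E, no K | yes | no | no | no |
| 3. T (clear), E, K | yes | no | no | yes |
| 4. D and P, timing not clearly reasonable | yes | yes | no | no |

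- Row 1: the event meets both Possibly and Probably on either reading, and the section gives no tie-break. On reading A every Probably event is also Possibly, because timing alone is enough.
- Row 2: this event has stronger evidence than row 1 but cannot be rated Probably. It is Possibly on reading A and has no category on reading B. Not related and Unlikely related do not fit either, since timing is reasonable and no other cause remains.
- Row 4: Possibly can be met without Probably, so the containment runs one way.

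**Object of the rating.** The section headings numbered 8.2 to 8.5 use study drug for E6201, and 8.7 covers dabrafenib separately. Yet 8.7.1 also applies the term to dabrafenib, and 10.3.1.4 allows for more than one study drug. Take a fever that the investigator attributes to dabrafenib. If study drug means E6201, dabrafenib is another drug and the fever is Not related. If it means the regimen, the fever is related. Both codings comply with 10.3.1.5.2.

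**Subjects affected.** Section 5.2 gives 6 to 12 subjects in the combination run-in and up to 18 in expansion.

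- Counted separately: 6 + 18 = 24 to 12 + 18 = 30. This matches the stated total less the 4 monotherapy subjects (28 − 4 = 24; 34 − 4 = 30).
- With the 6 MTD run-in subjects counted within the 18, as 5.1 says: 6 + 18 − 6 = 18 to 12 + 18 − 6 = 24.

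The range is therefore 18 to 30 if all 18 expansion places are filled.

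**Would a one-word change do?** If Probably read T and E, its events would still meet Possibly on reading A, and Probably would differ from Definitely only in the known pattern and the clarity of timing. Possibly has to change as well.

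**The case against.** The strongest reply is that little depends on Possibly versus Probably. The DLT criteria do not use the five categories. SAEs within 28 days of the last dose are reported whatever the relationship. If the tables pooled the upper three categories as related, the overlap would not change the count, and the earlier E6201 solid tumor study in 3.1.4 did combine possibly and probably. Read generously, the wording on other causes also runs in order: presumable, then not excluded, then ruled out. On attribution, the dose rules and the late-SAE rule already name each drug, action taken is recorded for each event, and safety is summarized separately by phase.

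Much of this stands, and it limits the point. A reader might infer that the whole scale is inverted or that the tables cannot rank certainty at all. The documents do not support that: Not, Unlikely and Definitely are in the expected order, and the fault lies at the boundaries of the upper three. A reader might also infer that the trial's data cannot separate the two drugs. The CRF is not in the documents and may collect a rating for each drug, so this is unproven. Nor would a dabrafenib fever enter the E6201 monotherapy profile, because the phases are reported apart.

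What the reply does not remove: row 2 remains misplaced even on the generous reading, no pooling rule is stated for this trial, separation by phase does not split the drugs within the combination, and a later analysis plan cannot recover a rating that was never collected.

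**Conclusion.** The point holds in limited form. Probably related is wrong as written: it bars events whose other causes were excluded, and as punctuated its events all meet Possibly too. Those two of the five categories are not reliably distinguishable in the relationship tables. Separately, the causality section and the planned tables do not specify attribution by drug for the 18 to 30 combination subjects, although other sections rely on it, and the clause on another drug permits opposite codings of the same event.

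The effect is on descriptive safety reporting only. The primary endpoint, sample size and DLT rule are unchanged. The replacement rule in 6.3.2 does refer to events not related to drug, but it does not cite the five categories, and nothing here rests on it. The verdict assumes that investigators apply 10.3.1.5.2 as printed and that no CRF instruction overrides it. How many events would be misclassified cannot be estimated from the documents.

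**What to change.** In 10.3.1.5.2:

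- Define study drug, and say whether the partner drug counts as another drug under Not related.
- Reword Probably so that other factors are unlikely to be the cause.
- Limit Possibly to events for which other factors are also presumable.
- State that an event meeting Definitely is rated there, so that the upper three categories are exclusive and ordered. The row 2 event then falls under Probably.
- In the combination phases, rate each event separately for E6201 and for dabrafenib.

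In 11.3.1.1, tabulate TEAEs and SAEs by relationship to E6201, to dabrafenib and to either, and state which categories count as related. Align the synopsis wording.

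The cost is a text change, one extra CRF field and one extra set of tables, with slightly more work for sites. Attribution between two drugs given together remains a judgement. The change is best made before more combination data accrue, because ratings by drug made at the time are hard to reconstruct later.

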#### 10.3.1.6. Adverse Event Reporting

Each AE is to be reported by the investigator as serious or non-serious according to the definitions above. This classification determines the regulatory reporting procedures to be followed as described in Table 10.

**Table 10: Reporting Guidelines for Adverse Events** 

Gravity of AE	Reporting Time to Spirita Oncology	Type of Report
Serious	Within 24 hours after the site becomes aware of the event	Initial SAE Report
Non-Serious	Per AE CRF module	Completed AE CRF Module

Any SAE, regardless of relationship to investigational therapy that occurs within 28 days following the last dose of study drug must be reported to the Medical Monitor within 24 hours after the site becomes aware of the event. The investigator is encouraged to discuss with the Medical Monitor any adverse experiences for which the issue of reportability is unclear or questioned. The initial report should be followed by submission of a more detailed SAE Report when follow-up information is available.

If the SAE occurs more than 28 days after the last dose of study drug, SAEs should be reported only if considered related to E6201 or dabrafenib. In the event of subject death, the reason for death should be recorded as the SAE, with 'death' recorded as the outcome on the SAE CRF module.

Confidential 54
December 31, 2019 Protocol Amendment 4

The SAE also will be recorded as an AE on the AE CRF module. Note: the SAE Report is different from the AE CRF. In areas of both forms where the same data are reported, the forms will be completed in a consistent manner. For example, the same term should be used for the AE on both forms, with the same start and stop dates, action taken, outcome, etc. A checkbox on the AE CRF module for whether the AE resulted in an SAE, will link the two types of report for a given event.

An SAE Report should be prepared with as much available information concerning the event as possible so that a written report can be filed with the appropriate regulatory authorities. If causality cannot be determined definitively at the time of the SAE occurrence, it is important to notify Spirita Oncology within the timeline stated above, and to attribute the relationship as 'Not Assessable' (only applicable for the initial SAE Report). When new significant information is obtained, and the outcome and attribution of the event is known, the investigator will communicate this in a follow-up SAE Report. This relevant information will be provided in a timely manner to allow reporting to regulatory authorities within the required reporting period. Any SAE follow-up information requested by Spirita Oncology should be provided in a timely manner.

As necessary, the SAE Report should be accompanied by relevant pages from the CRFs, e.g., medical history, AEs, concomitant medications. Additional information may be requested by Spirita Oncology in an expedited manner to ensure that the initial reporting of the SAE made to the regulatory authorities complies with the required time frame. Spirita Oncology may be required to collect and report additional information to the regulatory authorities in a follow-up report, containing a final evaluation of the event, including copies of hospital reports, autopsy reports, or other relevant information.

